The following sample size calculations were based on comparison of the mean difference between groups (or arms) on a continuously measured outcome (or continuous variable). The sample size was fixed and detectable EF (or Cohen's D) was calculated. The detectable point difference for a continuous outcome was then calculated by multiplying EF and SD for the outcome measure.

Specific Aim 1.1: to test the hypothesis that HIN performance correlates with CAP amplitudes in anesthetized humans with Normal OHC function.

n = 52 subjects

Statistical Methods: described in detail in the Data Analysis section of the Research Strategy.

- 1. ANOVA to determine whether anesthetized subjects exhibit less variability than nonanesthetized subjects
- 2. Univariate and multivariate models to determine the relationship between mean CAP amplitudes and the other independent variables listed in Table 3 in all subjects
- ANCOVA or the regression model with indicator variable for Difficulty HIN vs. No Difficulty HIN groups will be utilized to compare statistically significant differences in anesthetized CAP amplitudes between the two groups
- 4. Cognitive and central auditory processing will be similarly analyzed to control for higher order effects on HIN
- 5. Multivariate regression models will be used to examine the interaction effect of two HIN groups with other independent variables (age and gender for example) on the dependent variable of mean CAP amplitudes

Power analysis: An ANCOVA model with 80% power on a continuously measured outcome assuming a significance level of 0.05 and a two group sample size of 52 (n=26 in each of the Difficulty HIN vs. No Difficulty HIN groups) will detect an effect size (EF) of 0.8 or above. We will able to detect a trued difference of 0.13 μ V between two groups for the primary outcome of CAP amplitude assuming our current standard deviation of 0.166 for CAP amplitudes (triptodes) measured in the 57 subjects with PTA<12.5 dB HL in our existing database.

This effect size is less than desired for a large clinical trial. However, this size is appropriate given that the aim is to determine which method is the most effective in accurately measuring CAP in humans. Further, it is similar to the sample sizes of persons with $_{hf}$ PTA < 12.5 dB HL in the database of our existing clinical trial using triptodes (n= 57) and TM wick electrodes (n= 59) in unanesthetized humans to which this comparison will be made. The ensuing experiments will increase the subject size and reduce the EF.

Specific Aim 1.2: to test the hypothesis that HIN performance is primarily governed by OHC, rather than AN function.

n = 600 subjects

Statistical Methods: described in detail in the Data Analysis section of the Research Strategy.

- subjects will be rank ordered by hfPTA, and either parametric or nonparametric coefficients of correlation will be run between subjective HIN difficulty, objective HIN assessments, OHC function, AN function, central auditory processing, and cognitive functions
- 2. a mixed effect model with variation between and within AN synaptopathy groups and OHC dysfunction groups (individual subjects will be considered as random) will be used to calculate:
 - a. the percent of variance contribution to HIN function
 - b. the variance component ratio of OHC dysfunction vs. AN dysfunction
- 3. univariate and multivariate models will be applied to the data as described in Specific Aim 1.1 to determine the relationship between mean HIN performance and the other independent

variables (Table 3) in all subjects in order to identify statistically significant factors that contribute to HIN performance

Power analysis: Using a mixed effect model with two OHC groups (Groups 2, 5; n=100 per group), two AN synaptopathy groups (Groups 1, 4; n=100 per group), and two mixed OHC and AH groups (Groups 3, 6; n=100 per group), we will be able to detect a minimum detectable variance component ratio of 0.45 on a continuously measured primary outcome with power of 80%.

Specific Aim 2: to determine whether specific strategies employed by HAs to optimize HIN performance effectively compensate for either OHC or AN dysfunction

n = 1,000 subjects

Statistical Methods: described in detail in the Data Analysis section of the Research Strategy.

- 1. subjects will be rank ordered by _{hf}PTA, and correlations will be calculated between _{hf}PTA and the remaining variables
- subjects within each group will be categorized by _{hf}PTA as either Normal (0-12.5 dB HL), Minimal SNHL (12.6-25 dB HL), or Mild SNHL (< 26 dB HL)
 - a. ANOVA will be used to determine statistically significant differences in objective HIN performance, OHC function, and AN function
- 3. ANCOVA will be run to compare these variables among HA feature or control groups

Power analysis: Again, using mean CAP amplitude as the primary outcome, two hundred (200) subjects per group with equal (100) number of subjects with or without difficulty HIN, we will be able to detect 0.28 EF difference among groups with 80% power and a significance of 0.05. This can be translated to a 0.046 SNR Loss difference on HIN performance (QuickSIN) measured by CAP amplitude (standard deviation= 0.166). For the experimental group and HIN difficulty interactions, we will be able to detect an EF of 0.325 which is equivalent to 0.054 μ V on CAP amplitude.

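### Aim 1.1 item 1 assigns ANOVA, a test of means, to the question whether CAP amplitude varies less under anesthesia

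*SAP*

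**What the plan says.** Item 1 of the Statistical Methods for Specific Aim 1.1 reads "ANOVA to determine whether anesthetized subjects exhibit less variability than nonanesthetized subjects". It names no response variable, no measure of spread and no variance test. The list is introduced by a pointer to the Data Analysis section of the Research Strategy, which is not part of the SAP.

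The comparators appear in the continuation of the Aim 1.1 power analysis. They are the sponsor's existing triptode (n = 57) and TM-wick (n = 59) subjects, "in unanesthetized humans to which this comparison will be made". The same paragraph defends the sample of 52 on the ground that "the aim is to determine which method is the most effective in accurately measuring CAP in humans".

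The only power calculation for Aim 1.1 concerns a mean difference between the two HIN groups of 26. It gives an effect size of 0.8, or 0.13 µV at an SD of 0.166 µV. No sensitivity is given for the variability comparison.

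**The concern.** One-way ANOVA on an outcome tests whether group means are equal and takes the group variances to be equal. If anesthesia reduces the spread of CAP amplitude and leaves the mean alone, the test should reject at about its type I error rate however large the reduction. If anesthesia shifts the mean and leaves the spread alone, the test can be significant, and under item 1 that result would be read as a variability finding.

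Nothing else in Aim 1.1 fills the gap. Item 1 is the only listed analysis that compares anesthetized with nonanesthetized subjects, and that comparison is part of the SAP's defense of n = 52.

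**Working it through.** **Which ANOVA is meant.** The SAP's opening paragraph says its "sample size calculations were based on comparison of the mean difference between groups (or arms) on a continuously measured outcome". In Specific Aim 2, item 2a, "ANOVA will be used to determine statistically significant differences in objective HIN performance, OHC function, and AN function", which is an ordinary comparison of group means. Where the SAP does intend an analysis of variances, in Specific Aim 1.2, it names a variance component ratio. ANOVA on the outcome itself is therefore the natural reading of item 1.

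**The SAP's own figure.** With 26 per group, two-sided α = 0.05 and 80% power, the noncentral t distribution gives a minimum detectable d of 0.79. Power at d = 0.8 is 0.807, and 0.8 × 0.166 = 0.133 µV. The stated 0.8 and 0.13 µV reproduce, but they concern means.

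**Inputs for the variability question.**
- From the SAP: 52 anesthetized subjects (26 per HIN group), comparators of 57 and 59, SD 0.166 µV (triptodes), HIN-group difference 0.13 µV, α = 0.05.
- Assumed: normal data, one value per subject, two-sided tests, 0.166 taken as the within-group comparator SD, and SD ratios (anesthetized to comparator) of 0.5 to 0.75. The SAP gives no expected reduction. It also gives no SD for TM-wick electrodes, so the 52 vs 59 figures borrow the triptode value.

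Each scenario used 20,000 simulated trials. The simulation error near 5% is √(0.05 × 0.95 / 20,000) ≈ 0.15 percentage points.

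**Spread differs, means equal, no HIN-group difference.**

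| SD ratio | ANOVA, 52 vs 57 | ANOVA, 52 vs 59 | Brown-Forsythe, 52 vs 57 |
|---|---|---|---|
| 0.50 | 4.5% | 4.4% | 99.6% |
| 0.65 | 4.7% | 4.3% | 80% |
| 0.75 | 4.8% | 4.6% | 46% |

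**Means differ, spread equal.** A shift of 0.09 µV is 0.09 / 0.166 = 0.54 SD. With 52 vs 57, ANOVA rejects in 80% and Brown-Forsythe in 4.6%.

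**What 52 vs 57 can detect.** The exact two-sided F test (df 51, 56) has 80% power at a variance ratio of 0.460. The SD ratio is √0.460 = 0.678, that is, 0.166 falling to 0.678 × 0.166 ≈ 0.113 µV. One-sided, the ratio is about 0.71. Brown-Forsythe needs about 0.65. An observed ratio of 0.65 would have a normal-theory 95% confidence interval of about 0.50 to 0.86 (df 50, 55).

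**Effect of the HIN mixture.** If the two anesthetized HIN groups differ by 0.13 µV, each mean lies 0.065 µV from the overall mean. With a within-group ratio of 0.65 and an unmixed comparator, the apparent ratio is

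√((0.65 × 0.166)² + 0.065²) / 0.166 = 0.126 / 0.166 = 0.76.

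Brown-Forsythe power for 52 vs 57 at a within-group ratio of 0.65 is then:

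| Comparator | No centring | Anesthetized side centred by HIN group | Both sides centred |
|---|---|---|---|
| Unmixed | 41% | 83% | 79% |
| Also mixed (0.13 µV) | 62% | – | 79% |

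One-sided handling can also mislead when the within-group SDs are equal. Not centring rejects in 7.3% if only the anesthetized side is mixed. Centring only the anesthetized side rejects in 8.2% if the comparator has the same mixture.

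**The case against.** The strongest objection is that item 1 is a one-line summary that defers to the Research Strategy, and that ANOVA on absolute deviations from the median is itself an ANOVA and a valid test of spread. That could be what was meant. The point stands as a caveat on intent. It does not rescue the line, because nothing in the SAP signals that reading and the SAP's other uses point to means. If it was intended, the remedy is to write it down.

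A second objection is that variability might mean repeat-measurement error within a subject, which the language about accurate measurement could suggest. The magnitudes above would then not apply. Between-subject SD is the more natural reading, because the only SD given is taken across the 57 database subjects, but the SAP should say which is meant.

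The objections to the illustrations also stand in part. The TM-wick SD is assumed, the fall to 41% depends on an unmixed comparator, and the question is directional while the power figures are two-sided. None of these touches the main result: ANOVA stayed near 5% at every SD ratio tried.

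It is also true that item 1 does not test the stated hypothesis of Aim 1.1.

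**Conclusion.** The concern holds and should be fixed. On its natural reading, item 1 names a test that would miss even a halved SD (4.5% rejection) and could present a mean shift as a variability difference (80% rejection at 0.09 µV). With the same subjects, a test of spread has about 80% power at a within-group SD ratio of about 0.65 (Brown-Forsythe) or 0.68 (normal-theory F test). These ratios assume normal data, a comparator SD of 0.166 and one value per subject.

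The damage is confined to the supporting comparison of measurement methods. The contrast between HIN groups and its power statement are sound on this point.

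**What to change.** Replace item 1 with wording such as:

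> Between-subject variability of CAP amplitude in anesthetized subjects will be compared with the existing triptode (n = 57) and TM-wick (n = 59) groups by a Brown-Forsythe test (ANOVA on absolute deviations from the median). Deviations are taken within HIN-difficulty group, in the comparators too where HIN status is recorded. The SD ratio with its 95% confidence interval is reported for each comparison. ANOVA and ANCOVA are used for means only.

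Four additions belong with it:
- If within-subject, repeat-measurement variability is what was meant, say so and name a matching analysis instead.
- If HIN status is not recorded for the comparators, report centred and uncentred SD ratios as a range.
- State the sensitivity as assumption-based (about 80% power at a within-group SD ratio of about 0.65) and state whether the test is one- or two-sided.
- Note that between-subject SD mixes measurement error with true differences between people and scales with amplitude, and report the coefficient of variation alongside it.

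The cost is SAP wording and one added test. No subjects or measurements are added, and the comparators' HIN status is used only if it is already on file.

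### Aim 1.1 justifies n = 52 by a question about CAP measurement method that its non-concurrent database comparator cannot answer and its power calculation does not cover

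*SAP*

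**What the plan says.** Under Specific Aim 1.1 the SAP sets out "to test the hypothesis that HIN performance correlates with CAP amplitudes in anesthetized humans with Normal OHC function". The power analysis covers one comparison, with "n=26 in each of the Difficulty HIN vs. No Difficulty HIN groups", 80% power and a significance level of 0.05. It gives a detectable effect size of 0.8, translated to 0.13 µV with an SD of 0.166 from 57 triptode recordings in the existing database.

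The paragraph after the power analysis concedes that this is short of what a large trial would want. It calls the size acceptable because "the aim is to determine which method is the most effective in accurately measuring CAP in humans". It adds that the size resembles the normal-hearing sets in an existing trial's database, "using triptodes (n= 57) and TM wick electrodes (n= 59) in unanesthetized humans to which this comparison will be made", and that later experiments will enlarge the sample.

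The analysis bearing on this comparison is Statistical Methods item 1: "ANOVA to determine whether anesthetized subjects exhibit less variability than nonanesthetized subjects". It names no electrode, cohort or HIN term. Item 2 adds models of CAP amplitude on the Table 3 variables in all subjects. Detail is referred to the Data Analysis section of the Research Strategy.

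**The concern.** The Aim has two statements of purpose. The sample size is calculated for one (Difficulty vs No Difficulty HIN) and defended by the other (which method measures CAP best).

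The second purpose lacks a design that could deliver it. The anesthetized recordings come from the new sample and the unanesthetized ones from an existing trial's database. Any difference in mean or spread could come from anesthesia or from whatever else differs between the cohorts and periods. Item 1 as written also leaves open which electrode set is the comparator and whether HIN status is taken into account.

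Even a clean comparison of spread would not settle accuracy. Spread across people combines measurement error with true differences in CAP, and the true differences are what Aim 1.1 wants to relate to HIN. A method that lost signal could show less spread.

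At stake is a conclusion about the best recording method that could not be attributed to anesthesia.

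**Working it through.** **1. The plan's own figure.** Inputs from the Aim 1.1 power analysis: 26 per group, effect size 0.8, α = 0.05 (sidedness not stated; two-sided assumed), SD 0.166.

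- Normal approximation: n per group = 2(1.960 + 0.842)² / 0.8² = 24.5, so 25, against 26 planned.
- Noncentral t: noncentrality = 0.8 / √(1/26 + 1/26) = 2.88 on 50 df; power 80.7%. Minimum detectable effect at 80% power: 0.79 SD.
- Translation: 0.8 × 0.166 = 0.133 µV, stated as 0.13.

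The figure reproduces, for the HIN comparison.

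**2. The method comparison, for which no power is given.** Inputs: 52 anesthetized subjects against 57 (triptode) or 59 (TM wick). The SD of 0.166 is a triptode value; using it for TM wick is an assumption.

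- Means: noncentrality = d / √(1/52 + 1/57) = d / 0.192; 80% power needs d = 0.542, or 0.542 × 0.166 = 0.090 µV. Against 59: d = 0.538, or 0.089 µV.
- Spread: for SD ratio r (anesthetized to unanesthetized), two-sided F-test power = P(F < F₀.₀₂₅/r²) + P(F > F₀.₉₇₅/r²). 80% power needs r = 0.678 (51 and 56 df) or 0.680 (51 and 58 df), an SD of about 0.113 against 0.166.
- Item 1 does not say what quantity enters the ANOVA. Run on raw amplitudes with equal means and the anesthetized SD halved (52 vs 57, 20,000 simulated data sets), it rejected in 4.2%, about the nominal rate. That form does not test variability.

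No sample size in step 2 removes the confounding with cohort.

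**3. Illustrations of what electrode and HIN mix could do.** The inputs here are assumptions, not figures from the SAP.

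*Electrode.* Suppose the two database sets were pooled as 57 + 59 = 116 distinct persons and differed in mean by d SD. Pooled variance is multiplied by 1 + w(1 − w)d², with w = 57/116 and w(1 − w) = 0.25.

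| Assumed d | Variance factor | Apparent SD ratio with no anesthesia effect |
|---|---|---|
| 0.5 | 1.06 | 0.97 |
| 1.0 | 1.25 | 0.89 |
| 1.5 | 1.56 | 0.80 |

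*HIN mix, spread.* Suppose the true HIN difference equals the detectable 0.8 SD and 0.166 is the within-group SD. An even mix multiplies variance by 1 + 0.25 × 0.8² = 1.16 relative to a sample of one HIN category, so the SD rises by 7.7%, to 0.179. If the database has the same mix, there is no difference.

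*HIN mix, mean.* On the same assumption, a database with proportion p in the Difficulty group shifts the mean contrast by (0.5 − p) × 0.133 µV: 0.033 µV in size at p = 0.25 or 0.75, and 0.066 µV at p = 0 or 1. The detectable mean difference from step 2 is about 0.09 µV.

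**The case against.** The strongest reply is that the stated hypothesis and the only powered comparison lie wholly within the anesthetized sample. The database does not touch them, and the sample size is declared fixed. That stands, and it confines the point to the method comparison and the justification built on it.

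A reader might infer that item 1 pools both electrode types on the unanesthetized side. The SAP does not say so: it lists the two sets separately, and a three-group ANOVA fits the text as well. Nor does it say that the 57 and 59 are different persons, so 116 is not an established comparator size. That the database subjects differ from the anesthetized subjects is a strong inference, not an explicit statement.

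A reader might also infer that anesthesia can never be separated from electrode and HIN mix. The SAP does not support that either. It does not name the electrode used under anesthesia; if it is a triptode or TM wick, a matching database set exists. It does not give the HIN mix of the database; if HIN status was recorded, it can be adjusted for. Table 3 and the Research Strategy are not shown and may hold such terms. For these two factors the supportable statement is that item 1 as written does not separate them.

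Finally, the SAP never says that lower variability will be the criterion of accuracy. But item 1 is the only analysis listed under Aim 1.1 that explicitly contrasts anesthetized with nonanesthetized subjects, so the accuracy purpose has no other visible support.

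**Conclusion.** The point holds for the method comparison. On the text, anesthesia is confounded with cohort and period, and between-person spread cannot establish which method is more accurate. The stated power (effect size 0.8, 26 vs 26) belongs to the HIN comparison and does not cover the question used to defend n = 52. That HIN comparison is sound as calculated and is not in dispute.

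The variance and mean-shift figures show what electrode differences or an unequal HIN mix could do under assumed values. They are not demonstrated bias: the electrode and HIN-mix effects on spread can work in opposite directions, and either could be nil. The conclusion on cohort rests on no concurrent or within-subject unanesthetized recordings being planned elsewhere. The change is worth making, but it is moderate in weight: it alters what Aim 1.1 may conclude about method, not its sample size.

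**What to change.** In Statistical Methods item 1 of Aim 1.1:

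- Name the electrode used under anesthesia. Compare the anesthetized subjects with the triptode set and the TM wick set separately, taking the same-electrode set as the main contrast where one exists. If neither matches, state that electrode and anesthesia are not separable.
- Compare residual spread after fitting HIN group, with a procedure that tests spread. If HIN status is not available in the database, report that as a limitation.
- Keep the database limit of hfPTA below 12.5 dB HL, which the SAP already gives.

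In the paragraph after the power analysis, drop the justification based on accuracy of method, rest the sample size on the powered HIN-group comparison, and describe the method comparison as descriptive and non-concurrent.

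The cost is SAP wording and a subset analysis of existing data. The comparator for any one contrast becomes 57 or 59 (against at most 57 + 59 = 116, were the sets pooled and distinct), and the claim about method is weaker. The 26 vs 26 comparison is unchanged.

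### Specific Aim 2 defines Mild SNHL with a reversed inequality, so the three hfPTA categories overlap below 26 dB HL and omit everyone at 26 or worse

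*SAP*

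**What the plan says.** In the SAP, Specific Aim 2, Statistical Methods, item 2 states that "subjects within each group will be categorized by" hfPTA into one of three classes: "Normal (0-12.5 dB HL), Minimal SNHL (12.6-25 dB HL), or Mild SNHL (< 26 dB HL"). Sub-item 2a follows at once: "ANOVA will be used to determine statistically significant differences in objective HIN performance, OHC function, and AN function".

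The rest of Aim 2 uses hfPTA differently or not at all. Item 1 ranks subjects by hfPTA and correlates it with the other variables. Item 3 reads "ANCOVA will be run to compare these variables among HA feature or control groups". The aim has "n = 1,000 subjects", and its power analysis assumes "two hundred (200) subjects per group".

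The SAP does not define Mild SNHL anywhere else. It gives no order in which the three classes are to be applied and no rounding rule for hfPTA.

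**The concern.** The classes are meant to be exclusive and to run upward in hearing loss from Normal through Minimal to Mild. A Mild class of everything below 26 dB HL does not continue that sequence. It takes in both milder classes and leaves out the subjects it is meant to describe.

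Sub-item 2a is nested under this classification, so the classes are naturally read as the ANOVA factor, applied within each Aim 2 group. If the line is programmed as written, the subjects with the most hearing loss drop out and Mild cannot be compared with the other two levels. If the analyst repairs it silently, the boundary is chosen outside the plan, possibly after the data have been seen.

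**Working it through.** The plan states no figure for this point, so there is none to reproduce. The check applies the printed limits to hfPTA values and counts how many classes each value meets.

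**Inputs (SAP, Specific Aim 2, Statistical Methods, item 2).** "Normal (0-12.5 dB HL"), "Minimal SNHL (12.6-25 dB HL"), and Mild as < 26 dB HL with no lower limit.

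**Step 1: test values.** The last column uses Normal ≤ 12.5, Minimal > 12.5 to 25, Mild > 25.

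| hfPTA (dB HL) | Classes met as printed | Contiguous limits |
|---|---|---|
| -2.5 | Mild | Normal |
| 10 | Normal and Mild | Normal |
| 12.5 | Normal and Mild | Normal |
| 12.55 | Mild | Minimal |
| 20 | Minimal and Mild | Minimal |
| 25 | Minimal and Mild | Minimal |
| 25.6 | Mild | Mild |
| 26, 30, 40 | none | Mild |

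**Step 2: counts over a range.** The range 0 to 40 dB HL is used; the ceiling of 40 is illustrative.

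- Whole numbers (41 values): 26 values (0 to 25) meet two classes and 15 values (26 to 40) meet none. No value meets exactly one.
- Steps of 0.25 dB (161 values): 101 meet two classes, 57 meet none, and 3 (25.25, 25.5, 25.75) meet exactly one.

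**Step 3: does a coding order rescue the rule?**

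- Assign the first class that matches: Normal and Minimal receive the subjects within their printed limits. Everyone at 26 or worse is unassigned. Mild holds only strays: values below 0, between 12.5 and 12.6, or above 25 and below 26. In substance two of the three intended levels remain.
- Assign the last class that matches: everyone below 26 is Mild, Normal and Minimal are empty, and everyone at 26 or worse is unassigned. One level remains.

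**Step 4: possible exposure under literal coding.** The number of groups is 1,000 / 200 = 5. The SAP does not give the share of subjects at 26 dB HL or worse, so the shares below are assumptions.

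| Assumed share | Per group (share × 200) | Overall (share × 1,000) |
|---|---|---|
| 10% | 20 | 100 |
| 20% | 40 | 200 |
| 33% (one third) | 67 | 333 |

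**Step 5: alternative repairs of Mild alone.** This uses the 0.25 dB grid, with the other two classes as printed.

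| Mild defined as | In exactly one class | In none |
|---|---|---|
| > 26 | 157 of 161 | 25.25, 25.5, 25.75, 26 |
| ≥ 26 | 158 of 161 | 25.25, 25.5, 25.75 |
| > 25 | 161 of 161 | none |

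Under all three, values between 12.5 and 12.6 and values below 0 remain unclassified unless those limits are changed too.

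**Step 6: does the power statement depend on these limits?** With 200 per group, two-sided 5% significance and 80% power, the detectable standardised difference is (1.960 + 0.842) × √(2/200) = 0.280. This matches the stated 0.28 and uses no hfPTA class.

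**The case against.** The strongest reply is that this is a slip that corrects itself. Minimal ends at 25 and Mild is the next level up, so no sensible analyst would put everyone below 26 into Mild. On this view the coding scenarios and exposure counts describe something unlikely to happen. That largely stands, and it is why the point is minor. It does not settle the boundary: > 26, ≥ 26 and > 25 are all plausible readings, and they treat subjects between 25 and 26 differently.

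The sign could also be a misreading of the PDF. This cannot be excluded from the text alone, but nothing marks one here, and the same symbol reads sensibly in the hfPTA limits under Aims 1.1 and 1.2. A true > or ≥ would still leave the gap above 25.

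The SAP refers to a Research Strategy for the detailed methods, and that document is not at hand. It may hold a correct definition, but that would not make this line right.

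Two further reservations stand. Sub-item 2a does not name its factor; that the hfPTA classes are the factor is inferred from the nesting. And the boundary gaps matter only if hfPTA is recorded finely enough to fall in them. The SAP gives no resolution, though limits of 12.5 and 12.6 imply fractional values.

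**Conclusion.** The concern holds, as a minor point. The printed classes are neither mutually exclusive nor exhaustive, and no order of application gives the three intended levels. At most two usable levels remain, and subjects at 26 dB HL or worse are always lost.

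The effect is confined to item 2 and its ANOVA. The item 1 correlations use hfPTA as a ranked variable, item 3 compares hearing-aid feature or control groups without reference to these classes, and neither the power figures nor the OHC versus AN analysis of Aim 1.2 uses these limits.

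The logical defect rests on the printed text alone. Its consequence for the ANOVA rests on reading the classes as the factor in 2a. The number of subjects affected rests on assumed shares and arises only if the line is coded literally.

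**What to change.** Replace the line with contiguous, non-overlapping limits, for example: Normal hfPTA ≤ 12.5, Minimal > 12.5 to 25, Mild > 25 dB HL. This assigns every value exactly once, including those below 0, between 12.5 and 12.6, and between 25 and 26. If the sponsor prefers to keep a limit of 26, the SAP should state ≥ 26 together with a rounding rule for hfPTA that closes the gaps.

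The cost is one corrected line in the SAP. Sample size, power and trial conduct are unchanged.

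### Aim 2 asks about hearing-in-noise (HIN) benefit from hearing-aid (HA) strategies, but its primary outcome is CAP amplitude, which does not directly measure HIN, and no HIN outcome is validly powered

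*SAP*

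**What the plan says.** The objective of Specific Aim 2 in the SAP is "to determine whether specific strategies employed by HAs to optimize HIN performance effectively compensate for either OHC or AN dysfunction". The aim has "n = 1,000 subjects".

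Under Statistical Methods for Aim 2, item 2a reads "ANOVA will be used to determine statistically significant differences in objective HIN performance, OHC function, and AN function", and item 3 reads "ANCOVA will be run to compare these variables among HA feature or control groups". Neither item marks one variable as primary.

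The Aim 2 power analysis does: "Again, using mean CAP amplitude as the primary outcome, two hundred (200) subjects per group". It gives a detectable effect size of 0.28 at 80% power and a significance level of 0.05. It converts this to an SNR Loss difference of 0.046 on QuickSIN, using a standard deviation of 0.166. For the interaction of experimental group with HIN difficulty it gives an effect size of 0.325, expressed as 0.054 μV of CAP amplitude.

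The opening word of that power analysis points back to Aim 1.1, whose power analysis refers to "the primary outcome of CAP amplitude assuming our current standard deviation of 0.166 for CAP amplitudes (triptodes"). Aim 1.1 itself is "to test the hypothesis that HIN performance correlates with CAP amplitudes in anesthetized humans with Normal OHC function".

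**The concern.** In the Aim 2 objective, HIN performance is what the HA strategies are meant to improve, and OHC or AN dysfunction is the deficit to be offset. The outcome named primary is neither HIN performance nor an established stand-in for it. CAP amplitude suits Aim 1.1, which asks how CAP relates to HIN. Carried over to Aim 2, it leaves the stated question without a primary outcome that addresses it.

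The only sentence in the power analysis that mentions HIN attaches a QuickSIN label to a CAP figure. A reader could therefore believe that a 1,000-subject aim can detect a very small HIN difference, when its sensitivity on any HIN score has not been stated in the units of that score.

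**Working it through.** **Outcome against objective.** Four places in the SAP, set side by side:

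- Aim 1.1 treats HIN performance and CAP amplitude as two variables whose correlation is a hypothesis. Aim 2 cannot take that correlation as given.
- Aim 1.2 is "to test the hypothesis that HIN performance is primarily governed by OHC, rather than AN function". If CAP reflects AN function and this hypothesis is true, CAP would be a weak proxy for HIN.
- Aim 2, item 2a, lists objective HIN performance, OHC function and AN function as separate variables.
- The Aim 2 power analysis then makes CAP amplitude primary.

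The SAP does not spell out that CAP measures AN function. That reading follows from the term and from its use alongside AN function. The mismatch does not depend on it, because CAP is in any case not HIN performance.

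**The plan's effect size.** Inputs from the Aim 2 power analysis: 200 per group, power 80%, significance 0.05. Sidedness is not stated; two-sided reproduces the figure.

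- Detectable d = (1.960 + 0.842) × √(2/200) = 2.802 × 0.1 = 0.280 (0.281 with the t distribution).
- In the other direction, d = 0.28 needs 201 per group, and 200 per group gives 79.96% power.

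The 0.28 is right for one unadjusted pair of groups, on any continuous outcome, in units of that outcome's SD.

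**The plan's conversion.** The opening paragraph of the SAP sets the rule: effect size × SD of the outcome measure. The SD of 0.166 comes from Aim 1.1, where it is the SD of CAP amplitude.

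- 0.28 × 0.166 = 0.0465, which the SAP reports as 0.046 and labels SNR Loss.
- 0.325 × 0.166 = 0.0540, reported in the next sentence as 0.054 μV.

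The same SD gives microvolts in one sentence and SNR Loss in the one before it. The 0.046 is a CAP difference in μV.

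**What a QuickSIN figure would look like.** The SAP gives no QuickSIN SD. Assume SNR Loss is in dB, with an SD between 1 and 4 dB:

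- Detectable difference = 0.28 × 1 = 0.28 dB up to 0.28 × 4 = 1.12 dB.
- Detecting 0.046 dB would take about 7,419 per group (SD 1) to 118,698 per group (SD 4).

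**More than one pair.** 1,000 / 200 = 5 groups, if all groups have 200. Five groups give 5 × 4 / 2 = 10 pairs, so the Bonferroni level is 0.05 / 10 = 0.005.

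- Detectable d = (2.807 + 0.842) × 0.1 = 0.365 (0.367 with the t distribution), about 0.37 SD.
- Power at d = 0.28 is then about 49%.

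**Interaction.** As an illustration, take two HA groups of 200, each split equally by presence or absence of a dysfunction (an assumption: the SAP's 100/100 split is by HIN difficulty). The detectable difference between the two HA effects is 2.802 × √(4/100) = 0.560 SD.

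**The case against.** The strongest reply is that HIN performance is already compared among HA groups: item 2a lists it first and item 3 runs ANCOVA on these variables. In this document the term primary outcome is attached to Aim 2 only in the power sentence, and the next sentence speaks of QuickSIN. A label carried over from Aim 1.1 is at least as likely as a deliberate choice of CAP. The detailed methods are referred to a Research Strategy that is not at hand. All of this stands, and it limits the point to which outcome is primary and what is powered. It does not remove it: nothing in the document names HIN as primary, and the QuickSIN sentence contains no QuickSIN SD.

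A reader might infer something stronger: that a CAP comparison can never show compensation, because an aid works around the nerve without altering it, and that any CAP difference among HA groups would mostly be baseline imbalance. The document does not support this. It does not say whether CAP or HIN is measured aided or unaided, before or after HA use, or whether HA groups are randomised. It states no hypothesis about an HA effect on CAP in either direction.

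A reader might also conclude that a true HIN benefit would be detected only 5% of the time instead of 80%, or be reported as a negative trial. The first only restates the significance level after assuming no CAP effect. The second needs a testing hierarchy or success rule, and the SAP contains none.

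**Conclusion.** The point holds in a limited form. The primary outcome named for Aim 2 does not match its objective, and no HIN outcome is validly powered. A CAP difference among HA groups, or none, does not by itself say whether HIN performance was improved or a dysfunction offset.

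The effect size of 0.28 is correct for one unadjusted pair of 200-subject groups. The SNR Loss figure of 0.046 is not a QuickSIN quantity. On an HIN score the design detects 0.28 SD per pair, or about 0.37 SD under Bonferroni correction over ten pairs.

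Assumptions: two-sided testing, five equal groups for the 0.37, and a QuickSIN SD of 1 to 4 dB for any figure in dB. Whether 0.28 or 0.37 SD is an adequate target cannot be judged here, because the SAP gives neither a QuickSIN SD nor a meaningful difference. It therefore cannot be said that the present sample size is sufficient for an HIN outcome.

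**What to change.** In Aim 2:

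- Name objective HIN performance (QuickSIN SNR Loss) as the primary outcome, compared among HA feature and control groups.
- Make the interaction of HA group with OHC or AN dysfunction the test of compensation, since a main effect shows only HIN benefit. State how each dysfunction is defined, and give the detectable interaction on the QuickSIN scale.
- Keep CAP amplitude as the measure of AN function, used as a covariate or effect modifier.
- State when the QuickSIN score is taken and whether the aid is in use. Say how the analysis handles the 100/100 split by HIN difficulty, which is closely related to the new outcome.
- Delete the SNR Loss figure of 0.046. Give the detectable difference as 0.28 SD of QuickSIN for one unadjusted pair, or about 0.37 SD if ten pairs among five groups are Bonferroni-corrected. Convert to dB only with a sourced QuickSIN SD.

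The cost is SAP wording and a restated power paragraph; HIN performance is already among the analysed variables. The microvolt differences for Aim 2 would no longer describe the primary outcome. The stated sensitivity may look less favourable, especially for the interaction, and may prompt a second look at the sample size.
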